## 6 STUDY OBJECTIVES AND ENDPOINTS

**Table 6-1 Study Objectives and Endpoints**

Primary Objectives	Primary Endpoints

Safety objective
 
To assess the safety and tolerability of CLS12311 in patients with RRMS
	
Primary Safety Endpoint
 
The primary safety endpoint is measured by the number and severity of adverse events (AEs) and serious adverse events (SAEs) and/or worsening of disease measured by clinical (relapses) and imaging (number and size of brain MRI lesions) parameters.

Secondary Objectives	Secondary Endpoints

Safety objectives
 
To assess the safety and tolerability of each dose group of CLS12311
	
Safety Endpoints
 
 
• Incidence of treatment-emergent AEs (TEAEs) and treatment-emergent SAEs (TESAEs) (number and severity) in each dose group
 
• Number of confirmed relapses in the treatment phase in each dose group
 
• Changes in clinical measures of disease severity: EDSS, T25-FW, 9-HPT, SDMT in each dose group.
 

Exploratory Objectives	Exploratory Immunological and Biomarker Measures

To assess biomarkers indicating unwanted immune activation, and
 
To understand the mechanism/s of action of tolerance induction with peptide-coupled RBCs and to identify biomarkers for measuring immune tolerance induction
	
 
• Percentage of patients in each dose group showing a reduction of antigen-specific T cells against the protein(s) they responded to prior to study entry
 
• Changes in predefined serum- and cellular biomarkers including autoantigen-specific T cell responses that would indicate proinflammatory activation.
 

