Secondary endpoints	Safety endpoints 
 
Number and severity of TEAEs and TESAEs in each dose group
 
Number of confirmed relapses in the treatment phase in each dose group
 
Changes in clinical measures of disease severity (EDSS, 9-HPT, T25-FW, SDMT) following CLS12311 administration in each dose group
 

Exploratory endpoints	Exploratory immunological and biomarker measures 
 
Percentage of patients in each dose group showing a reduction of antigen-specific T cells against the protein(s) they responded to at the study entry
 
Changes in predefined serum- and cellular biomarkers including autoantigen-specific T cell responses that would indicate proinflammatory activation
 

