### **12.3.1 T Cell Reactivity**

Samples for antigen-specificity testing of T cells will be collected at scheduled visits as described in Section 14.

The goal is to assess the percentage of patients in each dose group showing an increase or reduction of antigen-specific T cells against the peptide/s or respectively target protein/s they responded to prior to study entry.

Blood collection, packaging and shipment will be described in the laboratory/logistics manual.

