## 14 VISIT SCHEDULE AND ASSESSMENTS

### 14.1 Procedures at Each Visit

#### 14.1.1 Baseline

Baseline evaluations and data collection will be used to determine eligibility for enrollment and to document patient clinical status prior to treatment. Information to be collected includes:

- Date of informed consent
- Demography
- Tobacco use
- Height and weight
- MS history (date of first MS symptom, date of first MS diagnosis, prior relapses, prior disease modifying therapies and symptomatic therapies)
- SARS-CoV-2 vaccination status
- Medical history (except MS history)
- Current medication except for MS (taken regularly for chronic conditions, or within the past 30 days)
- Physical examination
- Vital signs
- ECG (at least a 6-lead)
- Childbearing potential and ask patient if she is pregnant (pregnancy is an exclusion criterion)
- Urinary pregnancy test
- Central labs: Infectious Disease Screen (no extra blood sample needed)
- Hematology: complete blood count with differential and platelet count, Coombs test, coagulation studies (PT, PTT, INR) and sedimentation rate, blood group
- Clinical chemistry: Sodium, potassium, creatinine, eGFR, urea, total bilirubin, GGT, ALT/GPT, AST/GOT, alkaline phosphatase, total protein, albumin, lactate dehydrogenase, fibrinogen, CRP, iron, ferritin, haptoglobin, eGFR
- Urinalysis: specific gravity, pH, glucose, protein, ketones, nitrite, leukocytes and blood

- HLA typing HLA- [REDACTED] alleles (no extra blood sample needed; will be taken from blood collected for antigen specificity testing)
- Antigen specificity: collect 30 ml of EDTA blood
- Biomarker: collect one serum tube (5 ml)
- **Cranial MRI (contrast enhanced)**; (can be performed within 5 days after V1, latest on the same day prior to the blood donation)
- EDSS
- 9-HPT
- T25-FW
- SDMT
- Adverse events
- Assessment of inclusion/exclusion criteria

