#### 14.1.5 Visit [REDACTED] [REDACTED] [REDACTED] [REDACTED] [REDACTED] [REDACTED] [REDACTED] End of Treatment (EOT)/ Early Discontinuation (ED) visit

- Physical examination
- Vital signs
- Urinary pregnancy test
- Hematology: complete blood count with differential and platelet count, Coombs test, coagulation studies (PT, PTT, INR) and sedimentation rate
- Clinical chemistry: Sodium, potassium, creatinine, eGFR, urea, total bilirubin, GGT, ALT/GPT, AST/GOT, alkaline phosphatase, total protein, albumin, lactate dehydrogenase, fibrinogen, CRP, iron, ferritin, haptoglobin
- Urinalysis: specific gravity, pH, glucose, protein, ketones, nitrite, leukocytes and blood
- Antigen specificity: collect only 10 ml EDTA blood [REDACTED] and 30 ml EDTA blood [REDACTED]
- Biomarker: collect one serum tube (5 ml)
- **Cranial MRI (contrast enhanced)**; (can be performed +/- 5 days of the visit. If the MRI will be performed before [REDACTED], urinary pregnancy test has to be performed at the site prior to the MRI.
- EDSS
- 9-HPT
- T25-FW
- SDMT
- MS relapse assessment
- Concomitant medication
- Adverse events

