2.2.3 Exploratory Endpoints

- Percentage of patients in each dose group showing a reduction of antigen-specific T lymphocyte cells (T cells) against the protein(s) they responded to prior to study entry.
- Changes in predefined serum- and cellular biomarkers including autoantigen-specific T cell responses that would indicate proinflammatory activation

The analysis of immunological and biomarker data is outside the scope of this SAP.

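### The T-cell endpoint selects proteins on a positive entry result and then counts falls, so it could suggest tolerance induction when there is none

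*Protocol*

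**What the plan says.** Table 6-1 of the protocol defines the endpoint as the "Percentage of patients in each dose group showing a reduction of antigen-specific T cells against the protein(s) they responded to prior to study entry", and SAP 2.2.3 carries the same definition. The synopsis differs on timing and has "against the protein(s) they responded to at the study entry". Section 12.3.1 differs on direction: it aims at patients "showing an increase or reduction of antigen-specific T cells against the peptide/s" or target proteins, still limited to those the patient reacted to before entry.

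The schedule of events marks one antigen-specificity sample before treatment. Section 14.1.1 gives its volume: "Antigen specificity: collect 30 ml of EDTA blood". For follow-up, section 14.1.5 says "Antigen specificity: collect only 10 ml EDTA blood" at one time point and 30 ml at another; which visit is which is redacted.

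Section 16.1.3 plans descriptive summaries only, and the SAP adds nothing: "The analysis of immunological and biomarker data is outside the scope of this SAP". SAP 2.4 states that the study is not randomized, and every dose group receives coupled cells. Section 5.2.1 does not require T-cell reactivity for entry. Appendix 24.1 states that no validated assay exists for antigen specificity and related measures.

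**The concern.** A protein enters the count because its entry reading was high. Part of a high single reading is chance, from the assay or from the day, and that part tends not to recur. A later reading is then lower on average with no treatment effect at all. No untreated or uncoupled-only group shows how large this drift is, and the wording does not say how large a fall must be.

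The consequence is one of interpretation. Section 5.3 presents the testing of each patient's response as the way to show whether tolerance is achieved, and Appendix 24.1 wants the biomarker results to inform later studies and responder characteristics. In section 5.1.3.2, falls in peptide-specific responses in the earlier open-label trial of peptide-coupled red cells are already read as preliminary evidence of tolerance. A percentage that is high by construction could be read the same way.

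**Working it through.** The plan states no expected rate, assay repeatability or positivity cut-off for this endpoint, so there is no figure to reproduce. The check asks what an inert product would show.

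**Inputs from the documents.** One 30 ml pre-treatment draw; follow-up draws of 10 ml and 30 ml; 9 patients (2, 3 and 4 per dose group); no control.

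**Assumptions.** Test-retest correlation 0.5 to 0.9; share of readings called positive 50%, 25% or 10%; bivariate normal readings with no true change. The number of proteins is redacted.

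**Step 1: one selected protein.** Let L be the probability that a protein positive at entry reads below the cut-off at follow-up. If it does, it has fallen. If it stays above, the two readings are exchangeable and it is lower half the time. Hence

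P(lower) = L + (1 − L)/2 = (1 + L)/2,

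which cannot be below 50%. At a top-25% cut-off and correlation 0.7, L = 0.398 and P(lower) = 1.398/2 = 0.699.

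| Positive share | Correlation 0.5: L / any fall | 0.7 | 0.9 |
|---|---|---|---|
| Top 50% | 33% / 67% | 25% / 63% | 14% / 57% |
| Top 25% | 52% / 76% | 40% / 70% | 23% / 61% |
| Top 10% | 68% / 84% | 53% / 77% | 31% / 66% |

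**Step 2: a stricter rule.** With 30% positive and a log-scale SD of 0.5 to 1.0, requiring a fall of at least 50% gives 0.2% to 45% over the same correlations. The answer therefore depends heavily on the missing threshold.

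**Step 3: from protein to patient.** With five proteins tested, 30% positive and correlation 0.7, the any-fall rule among patients with at least one response gives 82% if one falling protein suffices, 73% if their mean must fall, and 53% if all must fall. With all patients in the denominator these become 68%, 61% and 44%. As an illustration, if nine independent patients each had a 70% chance, at least 5 of 9 would show a reduction with probability 90%.

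**Step 4: blood volume.** 10 ml is one third of 30 ml. I took Poisson counts with lognormal true rates, no change, and positivity at a count of 10 or more per 30 ml. If the read-out is a frequency per cell, the chance of any fall barely moves (59% at both volumes in one scenario; 62% at 30 ml and 61% at 10 ml in another). False loss of positivity rises in the same scenarios, from 24% to 35% and from 32% to 43%. Only an uncorrected raw count would be driven down strongly.

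**Step 5: counting both directions.** Take 100 protein tests at the top-25% cut-off and correlation 0.7. Of 25 positive at entry, 25 × 0.398 ≈ 10 turn negative. Because the two visits are exchangeable, about 10 of the 75 negatives turn positive. The net loss is zero, as it should be with an inert product and equal cell input.

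**The case against.** The endpoint is exploratory, with no hypothesis and 9 patients. It does not guide patient management, and Part B will not be run. The documents nowhere say that any fall counts. Correlation and cut-off are assumptions. All of this stands: it limits the harm to interpretation and makes the size conditional. It does not remove the selection, which every statement of the endpoint shares.

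Several stronger readings are tempting but unsupported:

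- **That an inert product would show most patients tolerized.** This needs an any-fall rule that the text never states. Under a 50% fall it was below half in every scenario run, and loss of positivity at the top-25% cut-off exceeds half only at correlation 0.5.
- **That the plan looks only for reductions.** Section 12.3.1 includes increases, and the second exploratory endpoint covers T-cell responses indicating activation. The fault is that these passages disagree, and that 12.3.1 keeps the same selection.
- **That this is the only planned read-out of tolerance.** Section 12.3.1.1 lists other tolerance markers, and 16.1.3 plans summaries of other cell populations.
- **That the 10 ml draw forces the result down.** For a per-cell frequency it does not, and the other follow-up draw matches baseline.

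Section 10.1.1 sends the buffy coat from the donation to the sponsor for research. It might offer a second pre-infusion sample, but no such use in this assay is stated.

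**Conclusion.** The point holds as a bias that could mislead, and it is worth correcting. Under the literal reading, in which any fall counts, an inert product gives a reduction in 57% to 84% of selected proteins over the assumed ranges. If loss of positivity is required, it gives 23% to 52% at a top-25% cut-off. These are per-protein figures; the per-patient percentage also depends on the number of proteins, the combining rule and the denominator, none of which is fixed in the text. The direction needs only imperfect repeatability and a single reading used twice. That double use is inferred from the schedule; the protocol does not state it. The smaller draw is a secondary issue of noise and false loss of positivity.

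**What to change.** Align the synopsis, section 6, section 12.3.1 and SAP 2.2.3 on one definition:

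1. Tabulate both directions, positive to negative and negative to positive, over all tested proteins by dose group. Show both columns and read the excess of losses over gains.
2. State one rule for the size of change and apply it equally to falls and rises. Name the time point and the denominator, including how patients with no response at entry are counted.
3. Use the same number of cells per protein at every visit, or restrict this endpoint to the 30 ml visits.

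Step 1 needs proteins that were negative at entry to be re-tested at follow-up, which the schedule does not guarantee; this should be confirmed. The comparison also assumes no assay drift between visits, since there is still no control.

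Splitting the Visit 1 sample into a selecting and a baseline aliquot is not a substitute. It removes assay noise only. At correlation 0.7 and a top-25% cut-off, the any-fall rate is still about 60% if half the non-shared variance is day-to-day biology, and 70% if all of it is.

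The cost is wording and one extra table, with no extra blood. The 10 ml visit may be lost for this endpoint, and the reported figure will probably be less favourable.

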## 7 STUDY DESIGN

Open-label, ascending-dose Phase Ib trial to evaluate the safety and tolerability of three doses of CLS12311 in patients with relapsing-remitting multiple sclerosis (RRMS).

The study will be conducted at approximately 12 sites in Europe.

The total duration will be at least 48 weeks for each participant and will include a total of 16 visits divided into two phases: an open-label treatment phase and a safety follow-up phase. The study phases are described in more detail in the following paragraphs.

Patient eligibility will be assessed during the Visit 1 (week 0) at baseline, where general patient and disease characteristics will be recorded. Patients who meet the criteria for enrollment will be sequentially allocated to one of the dose groups. The allocation to the dose group and the timing of treatment administration will be centrally coordinated to ensure appropriate safety assessments between dosing of patients. Hence, the time-period between [REDACTED] might vary between patients.

If safety and tolerability during the first treatment cycle, a subset of patients will receive a second administration of CLS12311 in a dose escalating second treatment cycle. Additional information on the rationale of the study design is given in section 5.2.3.

### 7.1 Open Label Treatment Phase: at least 17 weeks

The key measures, which have been implemented to ensure the safety of trial participants are briefly highlighted:

- Single ascending dosing starting with sentinel patient in each dose group
- An interval of at least 4 days between dosing of patients
- Safety assessments between dosing of each patient
- A scheduled DSMB meeting to assess safety of dosing after the last patient completes [REDACTED]
- Stringent criteria have been defined to trigger immediate DSMB safety assessments at any time during the trial
- Strict enrollment to allow safety assessment of the first treatment cycle prior to administration of second treatment cycle
- The second treatment cycle to be administered only after the safety of the first treatment cycle of the higher dose group has been confirmed
- The cumulative dose during second treatment cycle does not exceed the total dose of the first treatment cycle, for which safety had already been confirmed

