	
 
▪ Bag 1: [REDACTED] peptide-coupled RBCs (CLS12311)
 
▪ Bag 2: [REDACTED] peptide-coupled RBCs (CLS12311)
 
○ [REDACTED] 
 
▪ Bag 1: [REDACTED] peptide-coupled RBCs (CLS12311)
 
▪ Bag 2: [REDACTED] peptide-coupled RBCs (CLS12311)
 
 
 
 
manufactured from a single blood donation [REDACTED]
 
Second treatment cycle of CLS12311 will be given as follows:
 
 
• Group 1 (1 patient): 
 
○ [REDACTED] 
 
▪ Bag 1: [REDACTED] peptide-coupled RBCs (CLS12311)
 
▪ Bag 2: [REDACTED] uncoupled RBCs (placebo)
 
 
 
○ [REDACTED] 
 
▪ Bag 1: [REDACTED] uncoupled RBCs (placebo)
 
▪ Bag 2: [REDACTED] uncoupled RBCs (placebo)
 
 
 
 
manufactured from a single blood donation [REDACTED]
 
• Group 2 (2 patients): 
 
○ [REDACTED] 
 
▪ Bag 1: [REDACTED] peptide-coupled RBCs (CLS12311)
 
▪ Bag 2: [REDACTED] uncoupled RBCs (placebo)
 
 
 
○ [REDACTED] 
 
▪ Bag 1: [REDACTED] peptide-coupled RBCs (CLS12311)
 
▪ Bag 2: [REDACTED] uncoupled RBCs (placebo)
 
 
 
 
manufactured from a single blood donation [REDACTED]
 
• Group 3 (3 patients): 
 
○ [REDACTED] 
 
▪ Bag 1: [REDACTED] peptide-coupled RBCs (CLS12311)
 
▪ Bag 2: [REDACTED] peptide-coupled RBCs (CLS12311)
 
 
 
○ [REDACTED] 
 
▪ Bag 1: [REDACTED] peptide-coupled RBCs (CLS12311)
 
▪ Bag 2: [REDACTED] peptide-coupled RBCs (CLS12311)
 
 
 
 
manufactured from a single blood donation [REDACTED]
 

Statistical methods	
Sample Size Calculation	
As this is an exploratory Phase Ib study focusing on safety and tolerability, no formal sample size calculation has been performed.
 
The number of patients enrolled is considered sufficient to evaluate the safety and tolerability of CLS12311 and to collect preliminary exploratory biomarker data. The study is not powered for efficacy analyses.

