trial. The time interval between the first and second treatment is supported by preclinical safety studies of repeated dosing in monthly intervals over a period of three months. The time interval also reflects the safety of a [REDACTED] between autologous blood donations. During dose escalation of the second treatment cycle, the cumulative dose given in each dose group does not exceed the single dose, which has already been applied to patients of the next higher dose group as part of the initial treatment cycle (see 10.2.1). Consequently, the second treatment of patients in the lower dose group will be administered only after confirming the safety of the total dose given to patients in the single ascending dose. Hence, the safety of the total dose in the single/first treatment cycle is confirmed prior to administration of a second treatment cycle. Please refer to section 0 for more details on the study design.

In summary, the study is designed to provide a maximum of safety throughout both single dose escalation and second treatment.

Furthermore, the combination of clinical, MRI and immunological parameters provides a maximum of information as to safety, and tolerability of experimental treatment approaches and is therefore ideal for early-phase development [13].

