#### Single/First treatment cycle

The safety and tolerability of a single treatment cycle of CLS12311 will be assessed in an ascending dose study across three dose groups involving a total of 9 patients. Patients will be allocated to a low (total dose [REDACTED]; n=2), medium (total dose [REDACTED]; n=3) or high dose (total dose [REDACTED]; n=4)

Each dose group will start with a sentinel patient, who will inform about the safety of the treatment before dosing additional patients. To ensure the safety of dosing in the subsequent patient, a minimum time interval of four days will be established prior to dosing the next patient. This time frame is based on preclinical data showing that peptide-coupled RBCs are fully processed in the first 24h after infusion (see IB 5.3). However, due to the individual manufacturing process of each product and related logistics, only one patient will start treatment per week. Patients who fail to meet the eligibility criteria during screening will be replaced.

The treatment will start with the lowest dose group (2 patients). Higher dose groups (medium dose in 3 patients, high dose in 4 patients) will only be initiated once safety data from the preceding dose group, based on (S)AEs and relapses, has been confirmed by Sponsor's medical

expert(s). The corresponding data should be entered into the eCRF in timely manner, within 24 hours at the latest.

The first patient in each dose group (sentinel patient) will receive a single treatment of CLS12311. Sentinel patients will not receive a second treatment cycle. All sentinel patients will be followed with safety visits until Visit 16 (week 48) according to the schedule of visit (see section 4.1). The safety follow-up of sentinel patients will inform about the safety of the treatment prior to second dosing of other patients.

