### Second treatment cycle

The safety and tolerability of a second treatment cycle of CLS12311 will be evaluated in a subset of patients (n=6) from the single ascending dose study. Patients who receive a second treatment cycle in [REDACTED] of the trial will remain in the same dose group, i.e. low (total dose [REDACTED]; n=1), medium (total dose [REDACTED]; n=2) or high dose (total dose [REDACTED]; n=3). Hence, patients receiving a second treatment cycle will have the following total product exposure during the trial: low dose group [REDACTED] (n=1), medium dose group [REDACTED] (n=2) or high dose group [REDACTED] (n=3),

The [REDACTED] between the first and second treatment cycle is supported by preclinical safety studies of repeated dosing at monthly intervals over a period of three months. The safety of a [REDACTED] between autologous blood donations is also reflected in the dosing schedule.

The second treatment cycle will only be initiated after the safety of the first treatment cycle has been confirmed for the next higher dose group. The cumulative dose given to patients in the second treatment cycle will not exceed the dose of the first treatment cycle, which has already been administered to patients in the next higher dose group (see 5.2.3).

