### Safety Monitoring and DSMB Review

Safety and tolerability will be assessed using vital sign measurements, clinical laboratory tests (hematology, blood chemistry, and urine tests), physical examinations, and monitoring for (S)AEs and relapses.

Twice, after patient 3 and then after patient 6 have completed [REDACTED], the Sponsor's medical expert(s) will review safety data, including any serious and severe events judged to be related to peptide-coupled RBCs, to confirm safety of repeated dosing for patient 2 and for patients 4 and 5, respectively.

To ensure availability of safety data a stringent enrollment of patients has been defined (Figure 7-1).

Patients 1, 2 and 3 will be enrolled to receive a dose of [REDACTED] of peptide-coupled RBCs (patients 1 and 2) or [REDACTED] (patient 3) in the first treatment cycle (see 10.2.1). Only after confirmation of the tolerability and safety of the first treatment cycle in **patient 3** (single dose of [REDACTED]) at safety assessments visit in [REDACTED], the second treatment cycle of patient 2 (total cumulative dose of [REDACTED]) will be permitted.

Accordingly, patients 4, 5 and 6 will be enrolled [REDACTED]. Patients 4 and 5 will only receive the second treatment cycle (total cumulative dose of [REDACTED]) if the [REDACTED] safety data of **patient 6** (single dose of [REDACTED]) will support second dosing of CLS12311.

The second treatment cycle of the last three patients (patients 7 - 9) will be administered only after the safety and tolerability of second treatment cycle has been confirmed in **patients 4 or 5**. If safety data of [REDACTED] from patients 3 or 6 are not available due to prematurely discontinuation, second dosing of patient 2, 4 or 5 need to be postponed until sentinel patients are replaced and safety data are available.

After the last patient in the high dose group has completed [REDACTED] safety data (including MRI data, relapses and EDSS) of all patients will be evaluated by the DSMB.

[figure not shown]

If any of the treatment regimens are deemed to be unsafe, the DSMB may recommend protocol modifications or omit any of the dose levels (see Section 19.1.3). A substantial change will be submitted for approval by IRBs/ECs and the regulatory authorities, in accordance with CTR and Swiss ClinO (see Section 19.7).

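### The stated cap on cumulative second-cycle dose is not met for the three re-dosed high-dose patients, who reach twice the highest first-cycle dose in the trial

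*Protocol*

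**What the plan says.** The cap appears in four places.

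- **Protocol 7.1, list of safety measures:** "The cumulative dose during second treatment cycle does not exceed the total dose of the first treatment cycle, for which safety had already been confirmed". No dose group is named or excepted.
- **Protocol 5.2.3:** during second-cycle escalation, "the cumulative dose given in each dose group does not exceed the single dose, which has already been applied to patients" of the next higher group in their initial cycle.
- **Protocol 7.1, Second treatment cycle:** the same cap, again referred to the next higher group, with a timing rule: "The second treatment cycle will only be initiated after the safety of the first treatment cycle has been confirmed for the next higher dose group".
- **SAP 2.3.1:** repeats both the cap and the timing rule.

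The dosing is set out in the Synopsis (Study plan and Dosing), Protocol 5.2.2 and Protocol 10.2.1. There are three groups, and high is the top one: "Higher dose groups (medium dose in 3 patients, high dose in 4 patients) will only be initiated once safety data from the preceding dose group" has been confirmed. The first patient in each group is a sentinel and has one cycle only. The other six stay in their group and have a second cycle: one low, two medium and three high (patients 7-9).

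For patients 7-9 the Synopsis and Protocol 7.1 (Safety Monitoring and DSMB Review) give a condition of their own. Their second cycle "will be administered only after the safety and tolerability of second treatment cycle has been confirmed in" patient 4 or 5, both of whom are in the medium group.

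**The concern.** The cap is presented as a property of the whole second-cycle escalation. A reader of 5.2.3 or of the list in 7.1 would conclude that each re-dosed patient's total exposure had already been given to someone in a single cycle and found acceptable. The top group has no group above it, and its patients repeat their full dose, so the property cannot hold there.

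This is a first-in-human trial whose only primary objective is safety, and the claim concerns its highest exposure. Because the SAP carries the same sentence, it could pass into the clinical study report as a statement that cumulative exposure was always preceded by single-cycle experience. That would be untrue for half of the re-dosed patients.

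**Working it through.** **Step 1. Reproduce the plan's own count.** Group sizes are 2, 3 and 4, with one sentinel each who is not re-dosed. Second-cycle patients = (2 - 1) + (3 - 1) + (4 - 1) = 1 + 2 + 3 = 6. This agrees with the Synopsis.

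**Step 2. Coupled bags per cycle.** A cycle has two treatment days with two bags each. From the bag lists in the Synopsis:

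- Low: one coupled bag on the first day, none on the second. 1 + 0 = 1.
- Medium: one coupled bag on each day. 1 + 1 = 2.
- High: two coupled bags on each day. 2 + 2 = 4.

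The remaining bags in the low and medium groups are uncoupled cells. The second cycle has the same layout, so the two-cycle total is twice the one-cycle total.

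**Step 3. Compare with the cap.**

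| Group | Re-dosed patients | Two-cycle total (bags) | First-cycle total of next higher group (bags) | Cap met? |
|---|---|---|---|---|
| Low | 1 | 2 × 1 = 2 | 2 (medium) | Yes, ratio 1.0 |
| Medium | 2 | 2 × 2 = 4 | 4 (high) | Yes, ratio 1.0 |
| High | 3 | 2 × 4 = 8 | none exists | No |

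Against the largest first-cycle total anywhere in the trial, the high-group ratio is 8 / 4 = 2.0.

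**Step 4. How far this depends on redacted figures.** Let D be the high-group dose per cycle. Two equal cycles give 2D, and the highest first-cycle dose in the trial is D. The ratio is 2 whatever D is.

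**Step 5. Cell numbers, as an inference only.** One figure is readable: the Synopsis gives 6×10^11 as the low group's two-cycle exposure. If all coupled bags hold the same nominal dose, one bag is 6×10^11 / 2 = 3×10^11. The highest first-cycle dose is then 4 × 3×10^11 = 12×10^11, and patients 7-9 reach 8 × 3×10^11 = 24×10^11.

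**Step 6. Who is affected.** 3 of 6 second-cycle patients (50%), and 3 of 4 high-dose patients (75%).

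**Step 7. Does the specific condition for patients 7-9 stand in for the cap?** Patients 4 and 5 have a two-cycle total of 4 bags, and 4 / 8 = 0.5. The condition gives evidence about repeating a cycle, but only at half the cumulative exposure. Protocol 9.3.1 confirms that data from one of the two patients are enough. The high-dose sentinel, patient 6, has no second cycle and cannot supply the missing evidence.

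**The case against.** The strongest reply is that the cap limits itself. Protocol 5.2.3 and the second-cycle text in 7.1 refer to the next higher group, so they can only concern groups that have one. Patients 7-9 are given a different condition, which suggests that the authors knew the cap did not reach them. This may well be what was intended, but no text says so. The list entry in 7.1 is unqualified, and 5.2.3 speaks of each group.

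A second reply reads the list entry as limiting only the dose given within the second cycle. It would then be true of every group, because the cycle is simply repeated, but it would add no protection. It also does not fit Protocol 10.2.1, where the cumulative dose is the total over both cycles.

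A third reply is that other protections apply, and this one stands. The Synopsis lists safety reviews after each high-dose patient in the first cycle and at several points in the second. It also sets event-driven DSMB triggers. Protocol 7.1 uses sentinel follow-up to inform re-dosing, and Protocol 14.5 lists reasons to withhold an infusion in an individual patient. A DSMB meeting is scheduled after the last high-dose patient completes a visit whose number is redacted. It may precede the second cycle in patients 7-9, and the documents as released cannot settle this. A reader might infer that these patients were re-dosed without safeguards, or that patients 4 and 5 were the only check. The documents do not support either inference.

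It is also true that no endpoint, analysis set or estimate in the SAP uses the cap. SAP Final 2.0 followed the data review, so dosing is probably complete.

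**Conclusion.** The cap is stated without exception and is not met for patients 7-9, whose planned cumulative exposure is twice the highest first-cycle dose in the trial. The factor of 2 assumes only equal doses in the two cycles. The agreement for the low and medium groups, and the cell numbers 24×10^11 and 12×10^11, also assume equal nominal bags; the permitted range per bag is redacted.

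Two further readings go too far. The shortfall does not cover the whole high-dose group, because patient 6 has a single cycle. Nor does the cap bar patients 7-9 from a second cycle: the protocol schedules that cycle explicitly and gives it a condition of its own. The defect is a stated safety property that the design does not have at its highest exposure. The effect is on how exposure and safety are described, and no planned computation changes.

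**What to change.** The sponsor and DSMB should reconcile the cap statements (Protocol 5.2.3, the list and the second-cycle text in Protocol 7.1, and SAP 2.3.1) with the dosing and the re-dosing conditions (Synopsis, the safety-monitoring text in Protocol 7.1, and Protocol 10.2.1). Which rule governs the high-dose group is their decision, and this review does not propose one.

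They should also place on record which evidence supported giving the second cycle to patients 7-9, including whether the scheduled DSMB meeting came before it.

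The SAP and the clinical study report should describe exposure as the dosing gives it. In the low and medium groups, the planned two-cycle total equals the first-cycle total of the next higher group. For patients 7-9 it is twice the highest first-cycle total and has no single-cycle precedent in this trial. The report should use the doses actually given.

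The cost is wording in both documents (through an SAP addendum if the database is already locked) and one documented decision. The trial loses a favourable general statement about its escalation. No table or analysis has to be rerun.
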